### 2.3 CCS angina pectoris classification

Based on the following standard and combined with our concept of design, all

the eligible patients will be evaluated referring to the following standards by two researchers.

Classifications	Detailed contents
Class I:	Ordinary physical activity does not cause angina, such as walking, climbing
	stairs. Angina (occurs) with strenuous, rapid or prolonged exertion at work
	or recreation
Class II	Slight limitation of ordinary activity. Angina occurs on walking or climbing
	stairs rapidly, walking uphill, walking or stair climbing after meals, or in
	cold, in wind, or under emotional stress, or only during the few hours after
	awakening. Angina occurs on walking more than 2 blocks on the level and
	climbing more than one flight of ordinary stairs at a normal pace and in
	normal condition.
Class III	Marked limitations of ordinary physical activity. Angina occurs on walking
	one to two blocks on the level and climbing one flight of stairs in normal
	condition and at a normal pace.
Class IV	Inability to carry on any physical activity without discomfort anginal
	symptoms may be present at rest

### 2.4 Coronary angiography

All the included patients will undergo the coronary angiography to observe and record stenosis in coronary artery branches, including left main artery, left anterior descending artery, diagonal branches, left circumflex artery, obtuse marginal branch, acute marginal artery, right coronary artery and posterior descending artery.

All the collected data will be documented in the CRF. At the same time, the data will be saved in the computer folder which established beforehand.

#### 2.5 Recruitment procedures

The following scheme will be used to recruit participants with angina pectoris. Patients visiting the outpatient clinics and inpatient department in the department of Cardiology of the West China Hospital in Sichuan university will be informed by the cardiologist of the present trial. Research assistants will continue the enrollment process by screening eligible participants according to the inclusion/exclusion criteria. Participants will be included only if they meet the inclusion criteria and provide written informed consent indicating that they agree to every procedure of the trial and join in the trial willingly.

# 2.6 Sample size calculation

According to the diagnostic test sample size, ensuring the accuracy in the prediction, sensitivity is set 80% and specificity is 60%,  $\alpha = 0.05$ , the difference between the samples and the overall is  $\delta = 0.10$ . Considering a 15% dropout, 183 participants will be included in this trial finally.

$$n = Z_a^2 \times p \times (1-p)/\delta^2, (\alpha = 0.05, \delta = 0.1)$$

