#### 2. Methods

This part adopts the "single entry" cross-sectional study design. After the eligible patients recruited in group, the coronary artery stenosis will be evaluated through coronary angiography and the Canadian Cardiovascular Society(CCS) angina pectoris classification will also be evaluated at the same time. The degree of acupoint sensitization will be tested by the electronic Von Frey instrument by one professional acupuncturist.

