#### 2.8 Benefits and risks

This study is a single entry, cross-sectional and diagnostic studies. During this research, patients did not receive any therapeutic interventions, but stick to the original angina treatment plan. The main detection of acupoint sensitization concerned with stable angina pectoris by the VonFrey electronic measuring instrument: just put the instrument probe at the acupoint sensitization on the surface of the skin and record the data displayed in the instrument. In the process of operation, the sponsor will shoulder the economic burden caused by the occurrence of adverse events related to this study. Besides, the cost in the following examination may reduce considerably. In order to protect patient privacy, all the data are shrouded in secrecy, all relevant researchers must sign a confidentiality agreement before access to the data.

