### 3. Statistical analysis

Analysis were conducted to explore relationships between the degree of acupoint sensitization, the degree of coronary artery stenosis and CCS angina pectoris classification by SPSS20.0 software. For the collected data, the mechanical pain threshold of acupoint sensitization collected by Von Frey electronic measuring instrument and the degree of coronary angiography are continuous quantitative data. The grade of Canadian angina is qualitative data and specific correlation analysis method will be choose based on the type and distribution of collected data. Diagnostic value will be further analyzed in the final step.

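### The 183 in Section 2.6 matches two group sizes added together, but the study enrols one unselected cohort, so ±0.10 is not assured for both sensitivity and specificity

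*Protocol*

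**What the plan says.** Section 2.6 presents the calculation as one for a diagnostic test. The inputs are "sensitivity is set 80% and specificity is 60" (per cent), α = 0.05, and a precision described as "the difference between the samples and the overall is" δ = 0.10. It prints the usual precision formula for a single proportion, n = Z² × p × (1 − p)/δ², and ends: "Considering a 15% dropout, 183 participants will be included in this trial finally". It shows no intermediate sample sizes, does not say how the two values of p were combined, and gives no expected share of patients who are positive on the reference standard.

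The design is described elsewhere as a single cohort. Section 2.8: "This study is a single entry, cross-sectional and diagnostic studies". Section 2: "After the eligible patients recruited in group, the coronary artery stenosis will be evaluated through coronary angiography", with CCS class rated at the same time. Section 2.5: "Research assistants will continue the enrollment process by screening eligible participants according to the inclusion/exclusion criteria". No section sets a quota by stenosis or CCS class.

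**The concern.** Sensitivity is estimated only in reference-positive patients and specificity only in reference-negative patients. The printed formula therefore gives the number needed within each of those groups, not a total. The two numbers may be added if the design fixes both group sizes, as it would with separately recruited cases and controls. In a single-entry cohort the group sizes are observed, and the total must be large enough for whichever group turns out too small. That requires an assumed share of reference-positive patients, and Section 2.6 has none.

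At stake is the one design property that Section 2.6 offers in support of 183. If the share is not close to the one implied by the sum, one of the two accuracy estimates will have a wider confidence interval than stated, and the reader cannot tell which one or by how much.

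**Working it through.** **Inputs.** From Section 2.6: p = 0.80 (sensitivity), p = 0.60 (specificity), α = 0.05, δ = 0.10, dropout 15%, total 183. The section does not say whether α is one- or two-sided; z = 1.96 (two-sided) is used because it reproduces the total. The reference-positive share, π, is not in the documents and is varied below as an assumption.

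**Reproducing 183.**
- Sensitivity: 1.96² × 0.8 × 0.2/0.1² = 61.47, rounded up to 62.
- Specificity: 1.96² × 0.6 × 0.4/0.1² = 92.20, rounded up to 93.
- Sum: 62 + 93 = 155.
- Dropout: 155/0.85 = 182.35, rounded up to 183.

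Other readings tried do not give 183: sensitivity alone 62/0.85 → 73; specificity alone 93/0.85 → 110; one-sided z (44 + 65)/0.85 → 129; inflating by multiplication 155 × 1.15 → 179. The two-group sum is thus a reconstruction, but an exact one.

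**Splits that satisfy δ = 0.10 for both.** At least 62 positives and at least 93 negatives are needed.
- 155 evaluable: 155 − 93 = 62, so only 62 to 93 works, a share of 62/155 = 40.0%.
- 183 evaluable (no dropout): from 62 to 183 − 93 = 90 positives, a share of 62/183 = 33.9% to 90/183 = 49.2%.

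**Expected 95% half-widths at other shares.** For N evaluable patients, sensitivity: 1.96 × √(0.16/(N × π)); specificity: 1.96 × √(0.24/(N × (1 − π))). For example, N = 155 and π = 0.70 gives 108.5 positives and 46.5 negatives, hence 1.96 × √(0.16/108.5) = 0.075 and 1.96 × √(0.24/46.5) = 0.141.

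| Assumed share π | Sensitivity, N = 155 | Specificity, N = 155 | Sensitivity, N = 183 | Specificity, N = 183 |
|---|---|---|---|---|
| 20% | ±0.141 | ±0.086 | ±0.130 | ±0.079 |
| 30% | ±0.115 | ±0.092 | ±0.106 | ±0.085 |
| 40% | ±0.100 | ±0.100 | ±0.092 | ±0.092 |
| 50% | ±0.089 | ±0.109 | ±0.082 | ±0.100 |
| 60% | ±0.081 | ±0.122 | ±0.075 | ±0.112 |
| 70% | ±0.075 | ±0.141 | ±0.069 | ±0.130 |
| 80% | ±0.070 | ±0.172 | ±0.065 | ±0.159 |

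The N = 183 specificity at 50% is 0.1004 before rounding, just over the target.

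**The case against.** The best case for the plan has four parts.

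- **The split is inferred.** Section 2.6 prints neither 62, 93 nor 155, and gives δ once without saying that it applies to each measure separately. This is fair as a caution about intent. But one δ is set beside both accuracy values, and the consequence does not depend on how 183 was reached: that many patients give ±0.10 for both only within the window shown.
- **The miss may be small.** A 40% share is not a cliff edge. With 155 evaluable patients, 61 positives would give ±0.1004 for sensitivity, and between 30% and 50% the worse half-width never exceeds ±0.115. The large misses need shares of about 20%, or 70% and above, which the documents neither support nor exclude. This stands: no actual shortfall has been shown, only that the stated precision is not secured.
- **Diagnostic accuracy is not the main analysis.** The stated aim is correlation, and Section 3 leaves diagnostic value to the last step. The correlation analyses are indeed untouched. This limits the weight of the point but does not remove it, because sensitivity and specificity are the only basis given for the sample size.
- **The share depends on a cut-off that may be in an SAP not available here.** Section 3 says that the mechanical pain threshold and "the degree of coronary angiography are continuous quantitative data", so nobody is reference-positive until a threshold is chosen. That is correct, but no later choice of threshold makes 183 patients deliver ±0.10 for both measures outside the window.

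**Conclusion.** The point holds and should be fixed. The sums behind 183 are right in themselves; the fault lies in applying a two-group total to a single cohort. As written, Section 2.6 relies on an unstated 40% reference-positive share, which the design neither assumes nor secures. Near 40% the loss is minor; further away it grows, to ±0.141 for sensitivity at a 20% share or ±0.172 for specificity at 80%, with 155 evaluable patients. Which measure loses, and by how much, cannot be said, because the share could lie on either side of 40%.

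This rests on two-sided z = 1.96, on the protocol's own 80%, 60% and 15%, and on the reading of Sections 2, 2.5 and 2.8 that the reference-standard status is found after entry and not used to select patients. Confidence in the arithmetic is high.

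**What to change.** Keep 183 and restate what it delivers. Suggested wording for Section 2.6:

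> With 183 enrolled and 155 evaluable after 15% dropout, and assuming that [share or range] of patients are reference-positive on [condition], the expected 95% half-width is ±[x] for a sensitivity of 80% and ±[y] for a specificity of 60%.

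Here x is computed from 155 × share and y from 155 × (1 − share). The condition must be named, since it determines the share. If no single share can be justified, give a range. For illustration, 30% to 60% corresponds to ±0.115 to ±0.081 for sensitivity and ±0.092 to ±0.122 for specificity. The documents do not support that range over any other, so if values beyond it are plausible, the wider table should be used. Any suggestion that δ = 0.10 holds for both measures should go.

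The cost is wording only: enrolment, procedures and data are unchanged, and the stated precision of one measure becomes less favourable than ±0.10. Securing ±0.10 for both would instead mean enrolling the larger of 62/π and 93/(1 − π), divided by 0.85: 244 at a share of 30%, 219 at 50%, 365 at 70%. That is given for scale and is not proposed.

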# 2.7 Practitioners training

All researchers involved in this trial, all clinical physicians who enroll participants

and all assessors who collect data must attend training classes to make sure all practices in the hospital are generalized and standardized.

#### 2.8 Benefits and risks

This study is a single entry, cross-sectional and diagnostic studies. During this research, patients did not receive any therapeutic interventions, but stick to the original angina treatment plan. The main detection of acupoint sensitization concerned with stable angina pectoris by the VonFrey electronic measuring instrument: just put the instrument probe at the acupoint sensitization on the surface of the skin and record the data displayed in the instrument. In the process of operation, the sponsor will shoulder the economic burden caused by the occurrence of adverse events related to this study. Besides, the cost in the following examination may reduce considerably. In order to protect patient privacy, all the data are shrouded in secrecy, all relevant researchers must sign a confidentiality agreement before access to the data.

### 2.9 Safety and adverse event

For the sake of patient safety, prevention measures and emergency medical plans will include well-equipped treatment rooms, emergency department, cardiovascular specialist and first-line clinical physicians. All adverse events(AEs) associated with detection would be recorded in detail; these AEs concerning the short transient local skin discomfort include redness, itching and subcutaneous bleeding. On the other hand, the anti-anginal drugs (basic therapy) will be documented as well. Serious adverse events (SAE) are defined as death or life threatening events, which may require inpatient hospitalization, cause prolongation of existing hospitalization, or even result in persistent or significant disability/incapacity and need intervention to prevent permanent impairment or damage. If participants suffer any AE/SAE, researchers must immediately take measures to protect the safety of the patients, all details will be documented, and then report to the principal investigator and the ethics committee within 24 hours so that they can decide whether the patient should withdraw from the trial. The sponsor will ensure that meet the requirements of all laws and regulations of reporting procedures.

### 3. Statistical analysis

Analysis were conducted to explore relationships between the degree of acupoint sensitization, the degree of coronary artery stenosis and CCS angina pectoris classification by SPSS20.0 software. For the collected data, the mechanical pain threshold of acupoint sensitization collected by Von Frey electronic measuring instrument and the degree of coronary angiography are continuous quantitative data. The grade of Canadian angina is qualitative data and specific correlation analysis method will be choose based on the type and distribution of collected data. Diagnostic value will be further analyzed in the final step.

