### Abstract:

**Backgrounds**: this study, as the second part, aims to detect the correlation between the coronary artery stenosis, Canadian Cardiovascular Society(CCS) angina pectoris classification and the differential functional status of acupoints in distinguishing the severity of chronic stable angina.

**Methods:** We apply the cross-sectional study design to carry out the exemplary research in the aspects of disease diagnosis, in order to confirm the hypothesis "acupoint sensitization is associated with the severity of angina pectoris, and can contribute to the diagnosis of stable angina pectoris".

**Discussion**: This project will enrich the basic theory of TCM with a clear point of different functional acupoint status in the diagnosis of stable angina, which will offer important examples for the clinical application in disease diagnosis.

Keywords: Study protocol, diagnostic trial, stable angina pectoris

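### Does calling the CCS angina grade qualitative, and leaving the correlation method and covariates open, cost the study power or validity?

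*Protocol*

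**What the plan says.** Section 3 gives the aim of the analysis as relating acupoint sensitization to coronary stenosis and to CCS class. It states that the Von Frey threshold and the angiographic degree of stenosis "are continuous quantitative data". Of the third measure it says: "The grade of Canadian angina is qualitative data and specific correlation analysis method will be choose based on the type and distribution" of what is collected. It names no test, coefficient or covariate, and says that diagnostic value will be analysed last.

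Four other places bear on the point:

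- The Abstract gives the hypothesis: "acupoint sensitization is associated with the severity of angina pectoris, and can contribute to the diagnosis of stable angina pectoris".
- The table in Section 2.3 runs from Class I to Class IV by increasing limitation. Class II begins "Slight limitation of ordinary activity" and Class III "Marked limitations of ordinary physical activity".
- Section 2.8 says that patients "stick to the original angina treatment plan", and Section 2.9 that "the anti-anginal drugs (basic therapy) will be documented as well".
- Age (35 to 80) and sex appear in Section 2.1, as eligibility criteria only.

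**The concern.** Three features of Section 3 look weak.

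**Scale.** The hypothesis concerns severity, so the order of the CCS classes carries the information. Section 3 sets the grade apart from the continuous measures and does not mention its order. If that led to a comparison of four unordered groups, degrees of freedom would be spent on patterns the hypothesis does not contain, and the result would have no direction.

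**Timing.** The type of all three measures is already known, and a rank correlation would be valid for each whatever its distribution. Waiting for the data leaves room for choice that is not needed.

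**Confounding.** CCS class is a symptom grade taken on existing anti-anginal treatment, in men and women over a wide age range. A factor related to both pain threshold and severity could produce a correlation that would be read as acupoint sensitization.

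At stake would be power for the CCS comparison, the type I error rate, and the meaning of a positive correlation.

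**Working it through.** **1. Sample size (Section 2.6).** Inputs: sensitivity 0.80, specificity 0.60, δ = 0.10, two-sided α = 0.05 (z = 1.96), dropout 15%. With n = z²p(1−p)/δ²:

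- sensitivity: 3.8416 × 0.16 / 0.01 = 61.5, rounded up to 62
- specificity: 3.8416 × 0.24 / 0.01 = 92.2, rounded up to 93
- total 62 + 93 = 155 evaluable; 155 / 0.85 = 182.4, rounded up to 183

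The stated 183 is reproduced. It is a precision calculation for sensitivity and specificity and contains no correlation, so the choice of coefficient cannot change it.

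**2. Power if CCS were analysed as unordered.** By the noncentral chi-square at α = 0.05, a noncentrality of 7.85 gives 80% power on 1 df and 64.5% on 3 df; 10.51 gives 90% and 78.4%. At 155 evaluable, by the noncentral F with noncentrality N r²/(1−r²), and by simulation with four equal classes (4,000 runs each):

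| Assumed r | 1-df trend | 3-df unordered | Simulated Spearman | Simulated Kruskal-Wallis |
|---|---|---|---|---|
| 0.15 | 47% | 32% | – | – |
| 0.20 | 71% | 54% | 69% | 50% |
| 0.25 | 89% | 76% | 88% | 74% |
| 0.30 | 97% | 92% | 96% | 89% |

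The protocol gives no r, so these values are assumptions. With unequal classes (20, 45, 28 and 7%, also assumed) the simulated pairs are 69% and 51%, 85% and 72%, 96% and 89% for r = 0.20, 0.25 and 0.30. The loss is real for that test.

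**3. Is that the planned test?** Section 3 announces a correlation method chosen by data type. Spearman, Kendall tau-b and Pearson on scores 1 to 4 all use the order of the classes and test one parameter. A four-group comparison is not a correlation in that sense. The label is qualitative, not nominal, and qualitative data commonly include graded categories. Under a rank correlation the loss in step 2 is zero.

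**4. Choice after seeing the distribution.** In a null simulation (N = 155), Spearman alone rejected in 5.4% of runs. Taking the smaller p-value of Pearson and Spearman gave 6.5%; the smallest of Pearson, Spearman and Kruskal-Wallis gave 9.5%. These are worst cases in which the choice follows the p-value. Section 3 ties the choice to type and distribution, not to results.

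**5. Confounding.** If one factor correlates a with both measures and there is no other link, the spurious correlation is a². By Fisher's z with N = 155, where √152 = 12.33:

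- a = 0.2: r = 0.04, about 8% rejection
- a = 0.3: r = 0.09, about 20%
- a = 0.4: r = 0.16, about 51%

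The protocol supports no particular a.

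**6. Effect of adjusting for drugs.** Assume a reading–stenosis r of 0.25, a stenosis–drug r of 0.5, and drug use related to the reading only through stenosis, so that the reading–drug r is 0.25 × 0.5 = 0.125. The partial correlation is (0.25 − 0.125 × 0.5) / √[(1 − 0.0156)(1 − 0.25)] = 0.1875 / 0.859 = 0.22. Power at N = 155 falls from about 88% to about 78%.

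**The case for a change.** The strongest case for a change is that Section 3 states a rule rather than staying silent. It assigns a scale type without mentioning order, which the table in Section 2.3 plainly supplies, and it defers a choice for which all the needed facts are in hand. Read literally, the label does not exclude an association measure for unordered categories, and one sentence would exclude it. With no patient yet recruited, that sentence would cost nothing and could not be suspected of following the data.

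Much of this stands as comment on the wording. Ordinal is the better word, and naming Spearman or Kendall tau-b in advance is tidier. What does not stand is the step from loose wording to a loss: the wording permits an unordered analysis but neither plans one nor leads to one.

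The argument for adjustment is weaker. The absence of a covariate list is not a statement that the analysis is unadjusted. Only the anti-anginal drugs are expressly said to be documented. Adjusting for them in the main result is also open to dispute, because treatment may follow from severity, and conditioning on it can then remove part of the association sought (step 6). The stated hypothesis concerns association and diagnostic contribution, and for that the unadjusted relation is a legitimate quantity.

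**Conclusion.** No change to the plan follows. The CCS grade is ordinal by the protocol's own table, and Section 3 describes it loosely. The power loss, about 6 to 17 percentage points at 155 evaluable for assumed correlations of 0.15 to 0.30, belongs to an unordered test that the protocol does not name; under the rank correlation its wording allows, the loss is zero. The type I error figures of 6.5% and 9.5% require selection on p-values, which is not planned. The confounding figures rest wholly on assumed correlations, and covariates are normally settled in a statistical analysis plan, which is not at hand. The size of 183 is unaffected.

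This conclusion assumes that the analyst treats a four-step severity scale as graded when choosing a correlation, as is usual. A plan or report that tested CCS class as four unordered groups would bring the losses in step 2 into play.

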#### **Trial status**

This trial hasn't recruited any patients yet.

**Acknowledgments**: We acknowledge the West China Hospital of Sichuan university and Chengdu University of Traditional Chinese Medicine for their full support in facilities, recruiting and detecting. We also appreciate the help and efforts for all

research staffs participating in this trial.

**Financial support** This trial was supported financially by the Natural Science Foundation of China with No. 81590955.

